#### 8.1.3.1 Part A

Part A comprises Treatment Period 1, the Washout Period, and Treatment Period 2.

##### 8.1.3.1.1 Treatment Period 1

At the Day 1 Visit, the subject is required to continue to meet all inclusion and exclusion criteria ([Sections 9.1](#) and [9.2](#)) and continue to have stable PCD disease, in the opinion of the investigator. The first dose of inhaled study drug will be administered after randomization on Treatment Period 1 Day 1. Inhaled study drug should be taken according to instructions provided within the protocol. Study clinic visits will occur on Day 1 and Day 29 to allow for a full 28 days of treatment.

If the first dose of inhaled study drug administered in the clinic on Day 1 is taken in the morning, the second dose will be taken that evening. The last dose of the twice daily study regimen will be taken on the evening of Day 28 and no dose will be taken before the morning visit on Day 29.

If the first dose of inhaled study drug on Day 1 is taken in the clinic in the afternoon, a second dose will not be taken that evening. The last dose of the twice daily study regimen in Treatment Period 1 will be taken on the morning of Day 29, at least 4 hours before the Day 29 Visit.

Subjects should only take the inhaled study drug at a maximum of twice daily.

At Day 4 ( $\pm 1$  day), subjects will have a telephone call from the study coordinator or authorized site designee for safety purposes to ascertain if there have been any AEs. If necessary to follow up on a new medical problem, the subject may be asked to return to clinic.

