8.1 PRIMARY EFFICACY ENDPOINT AND ANALYSIS

Part A

The primary efficacy endpoint for Part A is the absolute change in ppFEV1 from study baseline, after 28 days of treatment in each Treatment Period of Part A.

The null hypotheses to be tested are that the mean absolute change from study baseline in ppFEV1 after 28 days of treatment is the same for 1) VX-371 in HS versus placebo; 2) VX-371 versus placebo; 3) VX-371 in HS versus HS alone. The primary assessment of efficacy will be based on the comparison of VX-371 in HS versus HS alone.

[figure not shown]
The primary efficacy analysis is based on a mixed-effects model. This model will include the absolute change from study baseline in ppFEV1 after 28 days (Visit Day 29 for Period 1 and Day 85 for Period 2) of treatment as the dependent variable, treatment and period as fixed effects, study baseline as a covariate, and subject as a random effect. The within-subject covariance will be assumed to have the compound symmetry (CS) structure. Denominator degrees of freedom for the F-test for fixed effects will be estimated using the Kenward-Roger approximation. No imputation of missing data will be done.

The estimated mean of the dependent variable, a 95% CI, and a 2-sided p-value will be provided for each treatment. There will be no adjustment for multiplicity. Similarly, the estimated between-treatment differences along with the corresponding 95% CI and 2-sided p-values will be presented.

[figure not shown]
A sample SAS code is provided below:

1006696
Parion Sciences Incorporated
CLEAN-PCD
SAP Version 1.0

Waterfall plot of the change from study baseline in ppFEV1 at Day 29 will be plotted by treatment group.

[figure not shown]

Summary statistics for the actual values and absolute changes from study baseline in pre-dose ppFEV1 will be summarized descriptively by treatment and visit based on Part A FAS.

In addition, the actual values and absolute changes at post-HS screening from pre-HS screening visit as well as actual values and absolute changes at Day 1 post-dose from Day 1 pre-dose in each period will be summarized based on Part A Safety Set and Part B Safety Set.

1006696
Parion Sciences Incorporated
CLEAN-PCD
SAP Version 1.0

[Redacted text block consisting of multiple lines of blacked-out content]

Part B

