	Treatment Period 1 (Day 1 through Day 29)					Treatment Period 2 (Day 57 through Day 85)					Treatment Period 3 ^a (Day 85 through Day 113)				
	Day 1 (±1 Day)	Day 4 Telephone Call (±1 Day)	Day 15 ^b Telephone Call (±1 Day)	Day 29 Visit (±3 Days)	Day 29 to Day 56 Washout (+3 Days)	Day 57 Visit (±1 Day)	Day 60 Telephone Call (±1 Day)	Day 71 ^b Telephone Call (±1 Day)	Day 71 ^b Visit (±3 Days)	Day 85 ^c Visit (±3 Days)	Day 86 Telephone Call	Day 87 Telephone Call	Day 99 ^{b,d} Telephone Call (-11 Days)	Day 99 ^{b,d} Visit (-11 Days)	Day 113 Visit (±3 Days)
Pre-visit reminder contact ^e	X			X		X			X						X
Part B informed consent/assent						X ^f									
Clinic visit	X		X	X		X		X	X		X	X		X	X
Safety telephone call ^g		X	X				X	X		X	X	X			
Inclusion/exclusion criteria review	X														
Randomization ^h	X														
Medical history	X														
QOL-PCD ⁱ	X			X		X			X						X
SGRQ ⁱ	X			X		X			X						X

^a Subjects will sign a new ICF (or assent if applicable) before the Day 85 Visit in order to continue into Treatment Period 3. If the subject does not sign the new ICF, Treatment Period 2 will end at Day 85 and the subject will continue through to the Safety Follow-up Telephone Call.

^b Day 15, Day 71, and Day 99 clinic visit required for subjects randomized prior to IDMC approval to change visit to a telephone call.

^c At the Day 85 Visit, subjects will remain in clinic for a total of 2 to 4 hours after dosing with study drug. The duration of the extended time for each subject (2 to 4 hours) will be left up to the discretion of the investigator. Post-dose safety assessments will be done prior to discharge from the clinic.

^d Day 99 Visit or telephone call may occur any time between Day 88 and Day 99. The clinic visit may be changed to a telephone call after approval from the IDMC.

^e Pre-visit reminder should be done 1 day before the visit, via telephone call, email, or text message, to remind subject to withhold short-acting bronchodilators for 4 hours prior to spirometry assessment performed at each visit, to withhold long-acting bronchodilators the night before the visit, and to administer study drug at least 4 hours before visits on Day 29, Day 85, and Day 113.

^f Subjects who participate in Part B will sign a new ICF for Treatment Period 3. This should occur at least 2 weeks prior to Day 85 to allow for delivery of study drug for Treatment Period 3.

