APPENDIX VI VISIT WINDOWS

The unscheduled or early withdrawal visit will be mapped to a scheduled visit for analysis using the date of collection/assessment as a basis to determine study day and then study day will be mapped to the intended visit. Table 8 and Table 9 below contain the analysis visit windows.

Table 8. Study windows

Study Period	Scheduled Visit/Day	Study Day Window	Analysis Visit
Period 1	Day 15 Visit	Day >1 - ≤ 22	Day 15
	Day 29 Visit	Day >22 - ≤ 36	Day 29
Period 2	Day 71 Visit	Period 2, Day >1 - ≤ 22	Day 15
	Day 85 Visit	Period 2, Day >22 - ≤ 36 ^a	Day 29
Period 3	Day 99 Visit	Period 3, Day >1 - ≤ 22	Day 15
	Day 113 Visit	Period 3, Day >22 - ≤ 36	Day 29

a: all assessments should happen before Part B dosing time.

For SGRQ, QOL-PCD [REDACTED] hematology, height and weight, [REDACTED] the following windows will be used:

Table 9. Study windows for Day 1 and Day 29 only

Study Period	Scheduled Visit/Day	Study Day Window	Analysis Visit
Period 1	Day 29 Visit	Day >1 - ≤ 36	Day 29
Period 2	Day 85 Visit	Period 2, Day >1 - ≤ 36 ^a	Day 29
Period 3 ^b	Day 113 Visit	Period 3, Day >1	Day 29

a: all assessments should happen before Part B dosing time.

[figure not shown]
b: visit windows for height and weight will only be applied for Period 1 and 2. Height and weight visit windows for Period 3 will be the same as table 6.

Once analysis visit windows are assigned, all visits, including scheduled visits, unscheduled visits, and early termination visits will be eligible for being flagged as the “analyzed record” within the analysis visit window. Note that the scheduled visit should match with the visit for which the visit window is defined. For example: If Day 29 visit falls in the visit window for Day 15, then Day 15 will be assigned to this visit. If no numerical measurement is available within a visit window, the measurement will be considered missing for the visit.

A subject’s individual analysis visit window could potentially contain more than one visit. In the event of multiple visits falling within an analysis visit window or in case of a

1006696
Parion Sciences Incorporated
CLEAN-PCD
SAP Version 1.0

Statistical Analysis Plan

tie, the following rules will be used in sequence to determine the “analyzed record” for the analysis visit window:

- the data closest to the scheduled day will be used.
- If there are multiple measurements with the same distance from the target day, the latest measurement will be used.

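### SAP Appendix VI gives the scheduled end-of-period visit no precedence, so a later unscheduled or early-termination ppFEV1 reading can replace it as the Day 29 value in the primary model

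*SAP*

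**What the plan says.** SAP Section 8.1 models the change from study baseline in ppFEV1 "after 28 days (Visit Day 29 for Period 1 and Day 85 for Period 2) of treatment". Appendix VI decides which reading supplies that value. Table 8 maps every reading from period Day 23 to Day 36 to the Day 29 analysis visit; study Days 85 and 113 are Day 29 of Periods 2 and 3.

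Appendix VI then says that "all visits, including scheduled visits, unscheduled visits, and early termination visits will be eligible for being flagged" as the record to be analysed. Where a window holds more than one reading, "the data closest to the scheduled day will be used". The second rule settles ties: "If there are multiple measurements with the same distance from the target day, the latest measurement will be used". Readings that are not selected appear only in listings.

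One limit is tied to dosing, a footnote to the Period 2 row: "all assessments should happen before Part B dosing time". No visible rule refers to the last dose of the period, and none ranks a scheduled visit above an unscheduled one.

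The timing comes from elsewhere:
- The schedule of assessments (Protocol Table 3-2, SAP Appendix IV Table 6) allows the Day 29 visit to move by 3 days either way, so it may fall on Days 26 to 32.
- For subjects who start in the morning, Protocol Section 8.1.3.1.1 says: "The last dose of the twice daily study regimen will be taken on the evening of Day 28". For afternoon starters the last dose is on the morning of Day 29.
- Subjects bring unused drug back at the Day 29 and Day 85 visits (Protocol Section 8.1.3.3).
- Washout begins on Day 29.

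**The concern.** The endpoint is meant to describe lung function at the end of a treatment period. The scheduled visit is the one designed to measure this, with bronchodilators withheld and dosing timed around it. Appendix VI can discard that reading for one taken days later, only because the later one lies nearer to Day 29 or equally near. By then the drug has been handed in.

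For such a subject the primary model uses a reading that may be off drug, while a valid end-of-treatment reading sits in a listing. The replacement may also be informative, because Protocol Section 8.1.6 provides for unscheduled visits to follow up changes in clinical status.

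**Working it through.** **1. Which later readings displace the scheduled visit.** Let s be the day of the scheduled visit (26 to 32) and u the day of a later reading (s+1 to 36). Under the distance and tie rules, u wins if |u − 29| ≤ |s − 29|, because u is the later of the two in a tie.

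| Scheduled visit s | Distance from Day 29 | Later days that win | Of these, after Day 29 |
|---|---|---|---|
| 26 | 3 | 27–32 | 30, 31, 32 |
| 27 | 2 | 28–31 | 30, 31 |
| 28 | 1 | 29–30 | 30 |
| 29 | 0 | none | none |
| 30, 31, 32 | 1, 2, 3 | none | none |

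For s = 30 to 32, every later day is further from Day 29 than the visit itself. Only a visit held 1 to 3 days early is exposed.

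**2. Whether the winning reading is off drug.** The documents do not say when dosing ends if the visit is early. If it ends when drug is returned at that visit, every day in the third column is off drug. If it runs to Day 28 or the morning of Day 29 regardless, only the last column is.

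**3. Which periods are open.** Period 1 has no dosing-related limit. In Period 2, a subject entering Part B takes the first Part B dose at the Day 85 visit, so the footnote shuts out readings after that dose. Subjects who do not enter Part B remain exposed. In Period 3 nothing closes the window.

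**4. Where a competing reading could come from.** No spirometry is scheduled between Day 29 and Day 57. The competitor must be an unscheduled visit (Protocol Section 8.1.6, where spirometry is not mandatory) or an early-termination visit (Protocol Table 3-3, which includes spirometry).

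**5. The plan's power, and an illustration.** SAP Section 3.5.1 gives SD 7, a 3-point difference, correlation 0, two-sided 0.05 and 10% dropout, with approximately 81% power for VX-371 in HS versus HS. With 100 × 0.9 = 90 subjects in Sequences 1 and 2:

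SE = 7 × √(2/90) = 1.0435; 3/1.0435 = 2.875; power ≈ Φ(2.875 − 1.960) = Φ(0.915) = 82.0%.

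The noncentral t with 88 df gives 81.2%, so the stated figure is reproduced.

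The documents give no rate of displaced readings. Purely as an assumption, let f be the share of VX-371 in HS records that are off drug, r the share of effect still present, and leave the HS records untouched. The difference becomes 3 × (1 − f(1 − r)).

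| f (of 90 records) | Difference, r = 0 | Power (normal), r = 0 | Difference, r = 0.5 | Power (normal), r = 0.5 |
|---|---|---|---|---|
| 2% (1.8) | 2.94 | 80.4% | 2.97 | 81.2% |
| 5% (4.5) | 2.85 | 78.0% | 2.925 | 80.0% |
| 10% (9) | 2.70 | 73.5% | 2.85 | 78.0% |

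These rows show how sensitive the result would be. They do not estimate what will happen.

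**The case against.** **It is rare.** Displacement needs an early scheduled visit and a second spirometry within a few days. This stands, and it limits the size of the point. It does not defend the rule, which drops a usable end-of-treatment value and gains nothing by it.

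**The SAP already ties the scheduled visit to its window.** Appendix VI does say that the scheduled visit should match the visit for which the window is defined. Its own example goes the other way: a Day 29 visit falling in the Day 15 window is relabelled Day 15. Date decides, and no precedence follows.

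**Using readings after discontinuation may be intended.** The full analysis set uses period data after one dose, and Protocol Section 9.5 keeps following subjects withdrawn from drug. That fits a treatment-policy approach, though no visible text declares one, and the endpoint is worded as after 28 days of treatment. The argument has force where no scheduled reading exists. It does not justify replacing one that does.

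**A reader might go further and infer that early-termination readings should be barred from the primary model**, picturing a subject who stops on Day 12 and enters as a 28-day result. The documents do not support this as a general description. The early-termination visit is due as soon as possible, and one held by Day 22 maps to Day 15. Someone stopping in the fourth week could enter as Day 29, but excluding such readings is an estimand choice. It would create missing values and lean harder on the protocol's assumption that dropout is at random.

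**Redaction.** Parts of SAP Section 8.1 and Table 2 are blacked out, so a relevant sensitivity analysis may already exist. It would not alter the record-selection rule for the main model.

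**Conclusion.** The point holds in a narrow form. Appendix VI, as written, selects the wrong record when the scheduled end-of-period visit is 1 to 3 days early and a later reading falls no further from Day 29. The mechanism follows directly from the stated rules and needs no assumption. Whether the replacement is off drug depends on when dosing ended for that subject.

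A reader might infer a material loss of power or a systematic pull towards no difference. Neither is supported. No rate of early visits or competing readings is given. Full loss of effect within a few days is the extreme case, since the protocol allows 28 days for FEV1 to return to baseline. HS is itself listed as an active substance, so off-drug HS readings could widen the difference between VX-371 in HS and HS. Few subjects are likely to be affected, and the size cannot be derived from the documents. The case for changing the rule is that it is wrong for those subjects and almost free to correct.

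**What to change.** Add to SAP Appendix VI:

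1. When the scheduled Day 29, Day 85 or Day 113 visit has a reading within the analysis window, that reading is the analysed record.
2. Unscheduled and early-termination readings are considered, under the existing distance and tie rules, only when the scheduled reading is missing.
3. For subjects without a scheduled reading, the main analysis keeps the present rule. Readings taken after the last dose of the period are flagged, and a sensitivity analysis of the primary model excludes them.

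The SAP should define the flag before unblinding, because even a regular morning visit on Day 29 follows the last dose by a night. The ±3 days is a visit-scheduling tolerance and was not set as a limit on time since dosing.

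The cost is a little extra programming and one further model run. No new data and no change in trial conduct are needed.
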